APPENDIX 3. DRAIZE SCALE

- *Study Personnel Instructions:* The modified Draize Scale as shown in the table below will be used for physical examination/rating of abnormalities at the injection site.
- The injection site should be examined for formation of both erythema and edema and results recorded in the Case Report Form. Evaluations of the injection site should be performed at 30±5 and 90±5 minutes after injection of study drug, and again at the end of the treatment visit at 180±5 minutes after injection of study drug. The 180-minute evaluation is still required even if glucose monitoring ends at an earlier timepoint.

Erythema Formation		Edema Formation	
Description	Score	Description	Score
No erythema	0	No edema	0
Very slight erythema Barely perceptible	1	Very slight edema Barely perceptible	1
Well defined erythema	2	Well defined edema	2
Moderate erythema	3	Moderate edema Raised approx. 1 mm	3
Severe erythema Beet redness to slight eschar formation	4	Severe edema Raised more than 1 mm and beyond exposure area	4

APPENDIX 4. GOLD SCALE

Hypoglycemia Awareness

Study Personnel Instructions: The following question should be answered by the subject at the Screening visit. This score is being collected for information purposes only; there are no scores that are considered exclusionary.

Subject Instructions: Please respond to the following question using the scale of 1-7 below. A minimum score of “1” indicates that you are always aware of an onset of hypoglycemia. A maximum score of “7” indicates that you are never aware of an onset of hypoglycemia.

To what extent are you aware of the onset of hypoglycemia?

1	2	3	4	5	6	7
Always	Almost Always	Often	Sometimes	Seldom	Almost Never	Never

Your score: _____

APPENDIX 5. SUBJECT STUDY DRUG ASSIGNMENT QUESTIONNAIRE

Study Personnel Instructions: The subject will be instructed not to talk with the study staff about their impression of which product he/she received until the end of the second treatment visit. Before leaving the clinic at the end of Visit 3, the subject should complete the questions below to indicate which study treatment they believe they received at each visit. Please ensure that the subject checks only one box for each question and does not select each treatment more than once. If the subject indicates they do not know, please ask them to make a guess.

Subject Instructions: Please respond to the following questions by picking only one of the two choices per question.

1a. Which study drug do you believe you received during your first treatment visit, which occurred before today's visit. (Check **one**):

Xeris Glucagon, G-Pen, administered by auto-injector

Comparator Glucagon, GlucaGen Hypokit, administered by needle and syringe

1b. Which study drug do you believe you received during your second treatment visit, which happened today. (Check **one**):

Xeris Glucagon, G-Pen, administered by auto-injector

Comparator Glucagon, GlucaGen Hypokit, administered by needle and syringe

1 LIST OF ABBREVIATIONS

Abbreviation or special term	Explanation
AE	Adverse Event
ALT	Alanine Aminotransferase
AST	Aspartate Aminotransferase
AUC	Area Under the Curve
BP	Blood Pressure
C _{max}	Maximum Plasma Concentration
ECG	Electrocardiogram
GCP	Good Clinical Practice
CRO	Contract Research Organization
HbA1c	Glycated hemoglobin
HBV	Hepatitis B virus
HCV	Hepatitis C virus
HIV	Human immunodeficiency virus
HR	Heart Rate
ICF	Informed Consent Form
IB	Investigator's Brochure
MedDRA	Medical Dictionary for Regulatory Activities
QTN	Quartesian LLC
PD	Pharmacodynamics
PGR	Positive Glucose Response
SAE	Serious Adverse Event
T _{max}	Time to Maximum Plasma Concentration
T1D	Type 1 Diabetes Mellitus
VAS	Visual Analog Scale
WHO	World Health Organization

2 INTRODUCTION

This documentation describes the planned data analyses for clinical trial XSGP-304 sponsored by Xeris Pharmaceuticals, Inc.

This SAP supersedes the statistical considerations identified in the protocol; where considerations are substantially different these differences will be identified. If additional analyses are required to supplement objectives described in the SAP, they may be performed and will be identified in the Clinical Study Report (CSR).

3 STUDY OBJECTIVES AND ENDPOINTS

3.1 Primary Objective

The primary objective of this study is to demonstrate that G-Pen 1 mg (test) is not inferior to GlucaGen Hypokit 1 mg (reference), in Type 1 diabetic (T1D) subjects in a state of insulin-induced hypoglycemia.

3.2 Secondary Objective

The secondary objective of this study is to evaluate the safety and tolerability of G-Pen 1 mg versus GlucaGen Hypokit 1 mg in the study population.

3.3 Endpoints

3.3.1 Primary Endpoint

For the primary endpoint, groups will be compared for rates of achieving a positive plasma glucose response (PGR), defined as either a plasma glucose concentration > 70 mg/dL (> 3.88 mmol/L) or an increase in plasma glucose concentration > 20 mg/dL (> 1.11 mmol/L), within 30 minutes of study drug injection.

3.3.2 Secondary Endpoints

For the secondary endpoints, treatment groups will be compared based on each of the following:

1. Rate of achieving a plasma glucose concentration > 70 mg/dL (> 3.88 mmol/L) within 30 minutes from injection of study drug.
2. Rate of achieving an increase in plasma glucose concentration > 20 mg/dL (> 1.11 mmol/L) within 30 minutes from injection of study drug.
3. Rates of positive symptomatic response, defined as relief of neuroglycopenic symptoms within 30 minutes from a decision to dose.
4. Rates of positive treatment response, defined as exhibiting either a positive plasma glucose response (within 30 minutes from injection of study drug) *or* a positive symptomatic response (within 30 minutes from a decision to dose).
5. Time to a positive plasma glucose response from injection of study drug.
6. Time to administer study drug from a decision to dose.

7. Pharmacodynamic (PD) characteristics of mean plasma glucose concentration (0 to 90 minutes post-dose), maximum observed concentration (C_{max}), time to maximum observed concentration (T_{max}), area under the concentration versus time curve from time 0 to 90 minutes (AUC_{0-90}), and area under the concentration versus time curve from time 0 to 180 minutes (AUC_{0-180}).
8. Time to (a) initial relief and (b) complete resolution of autonomic and neuroglycopenic symptoms of hypoglycemia from a decision to dose.
9. Time to resolution of the overall feeling of hypoglycemia from a decision to dose.
10. Safety endpoints, including adverse event (AE)/serious adverse event (SAE) rates, and changes in vital signs, laboratory variables, and physical exam/electrocardiogram (ECG) findings.
11. Tolerability endpoints, including: Draize scale scores for injection site erythema and edema as assessed by the investigator, and injection site discomfort and duration as assessed by subject questionnaire responses.

4 STUDY DESIGN

4.1 General Design

This is a non-inferiority, multi-center, randomized, active-controlled, single-blind, two-way crossover efficacy and safety in-patient study in subjects with Type 1 diabetes mellitus.

Subjects will be randomized to one of two treatment sequences below and will receive one dose within each treatment period separated by a washout period.

Table 1: Randomized Treatment Sequence

Treatment Sequence	Treatment 1	Treatment 2
1	G-Pen 1 mg	GlucaGen Hypokit 1 mg
2	GlucaGen Hypokit 1 mg	G-Pen 1 mg

In each period subjects will be confined to clinic at Day -1 before dosing, will undergo the following procedures and will be discharged at Day 1.

Day -1: Clinic arrival, assessments specified by protocol, evening meal in clinic.

Day 1:

- **Overnight monitoring (starting approximately at midnight) and Morning Procedures (starting at approximately 6 AM).**

Subjects will be monitored by glucose and will be given glucose and/or insulin to optimize plasma glucose levels. In the morning, plasma glucose (via YSI) will be assessed, and if > 270.0 mg/dL (> 15.0 mmol/L), the visit will be rescheduled after a minimum 3-day wait. Otherwise, the subject will be administered IV insulin to induce a baseline euglycemic steady state.

- **Baseline Euglycemic Steady State (early morning).**

Prior to starting the hypoglycemia induction procedure, the subject must have stable plasma glucose for at least 30 minutes at 95 ± 20 mg/dL (75 to 115 mg/dL [4.17 to 6.38 mmol/L]) at a stable IV insulin infusion rate varying no more than $\pm 20\%$ during which plasma glucose must be measured at least every 15 ± 2 minutes (i.e., at least 3 consecutive values in the target range at 0, 15, and 30 minutes).

The starting plasma glucose level (SG) will be determined as the average of the last 3 measurements taken over the final 30 minutes of the baseline euglycemic steady state period.

- **Hypoglycemia Induction Procedure (following baseline euglycemic steady state).**

Hypoglycemia will be induced by adding an initial IV bolus push dose of regular insulin diluted in normal saline until and further *insulin dose adjustments* specified in the protocol.

Initial IV bolus push dose will be calculated as 75% of the dose estimated to reduce plasma glucose from the subject's starting plasma glucose level (SG) to desired glucose level 54 mg/dL (3.0 mmol/L) based on the subject's self-reported glucose correction factor. This dose will be referred to as "first bolus (full bolus dose)" (BD1) subsequently:

$$\text{BD1 (mg/dL)} = [(\text{SG} - 54 \text{ mg/dL}) / \text{Correction factor}] \times 0.75.$$

- **Randomization.** Once the initial bolus dose of insulin has had time to take effect and the subject is observed to be in a controlled rate of glucose decline, the subject will be randomly assigned to one of the treatment sequences shown in Table 1.
- **Confirmation of Hypoglycemic Steady State.** Once the initial plasma glucose measurement < 54.0 mg/dL (< 3 mmol/L) is achieved, the IV insulin infusion will be returned to the rate established at the end of the baseline euglycemia steady state period. After 5 minutes, the IV insulin infusion will be stopped, and up to 3 confirmatory plasma glucose readings will be taken at subsequent 5-minute intervals to determine whether a hypoglycemic steady state has been reached.

A *hypoglycemic steady state* is defined as a confirmatory plasma glucose value ≥ 42 mg/dL (≥ 2.33 mmol/L) and < 54 mg/dL (< 3 mmol/L), and an 8-minute linearly extrapolated future plasma glucose value ≥ 42 mg/dL (≥ 2.33 mmol/L).

- **Decision to Dose.** Once the hypoglycemic steady state is confirmed, the Investigator will confirm that it is appropriate to administer study drug to the subject. The clock time of this "Decision to Dose" will be captured in the source documents. Decision to dose time is entered on the Induction CRF for each visit and will be used in the analysis.
- **Preparation and Administration of Study Drug.** Following a decision to dose, subjects were administered a subcutaneous injection around the umbilicus with either 1 mg GlucaGen Hypokit or 1 mg G-Pen.
- **Post-dose assessments.** Blood glucose levels will be monitored for up to 180 minutes post-dosing. Subjects will also complete a questionnaire about symptoms of hypoglycemia during the hypoglycemia induction phase and for up to 180 minutes after treatment with glucagon.

Plasma glucose levels and assessments of neuroglycopenic symptoms will be censored after the time of drug administration. This censoring is applicable only if the insulin is

restarted prior to the 180 minutes timepoint as per the following language in the protocol:

“After study drug administration and before 180 minutes post-dosing, if rising glucose levels are observed and if deemed medically necessary, insulin therapy or other medical intervention may be initiated by the Investigator.

- a. Such intervention is not recommended to occur before 90 minutes post-dosing of study drug.
- b. Plasma glucose data and assessments of neuroglycopenic symptoms will be censored after the time of intervention, per the statistical analysis plan.
- c. These interventions (such as insulin, carbohydrates, or a meal) prior to 180 minutes post study drug administration should be captured in the source documents, and further glucose measurements may be performed at the discretion of the Investigator.”

The specific hypoglycemia induction procedures and justification, and rules for interruption and termination of dosing are specified in the protocol.

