5.3.6.2 Secondary Endpoints

5.3.6.2.1 Pharmacodynamic (PD) Parameters

The PD endpoints will be derived from the individual glucose profiles. Pharmacodynamic characteristics, including:

- AUC_{0-90} and AUC_{0-180} : plasma glucose area under the concentration versus time curve for 90 and 180 mins from glucagon administration;
- C_{max} : Maximum concentration of glucose in plasma;
- T_{max} : time (in mins) when Glucose C_{max} is reached;

The following rules will be used for incomplete data:

- AUC: If there are missing data points before the last observed value, they will be extrapolated using the last two data points;
- AUC: If there are missing data points after the last observed value, they will not be imputed, and the AUC will be treated as not defined;
- If insulin starts after receiving glucagon, the glucose values post insulin start will be censored out and considered as missing. This is also considered a major protocol deviation.

Comparison between the treatments will be performed using a mixed model with treatment, period and treatment*period as fixed factors and subject as a random factor.

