6.5 Analysis of Primary Endpoint

The primary endpoint analysis will be based on the risk difference in rates of failing to achieve Positive Plasma Glucose Response (PGR) of G-Pen versus GlucaGen Hypokit and a 95% CI will be calculated. Non-inferiority will be declared if the upper limit of the 95% confidence interval for the difference in failure rates is $\leq 5\%$; where the absolute failure rate of G-Pen treatment is $\leq 5\%$. This analysis will be repeated for ITT, mITT and PP populations.

Subjects who are missing the primary endpoint for a study treatment will be considered as having a failure in the primary analysis for that treatment administration. This imputation will be conducted for both the ITT and the mITT populations. If a subject received the same two treatment administrations for both periods (Period 1 and Period 2), only the visit with the planned treatment received will be included in the primary analysis and the subject will be considered a failure in the primary analysis for the for unreceived treatment administration (ITT, mITT). For all other analyses, data will be included for only the planned treatment received in those analyses.

A sensitivity analysis will be performed for where all missing data will be considered a success and the same analysis as above completed.

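### SAP 4.1 starts censoring at study drug administration, against the protocol rule it quotes and SAP 5.3.6.2.1; programmed as written, it could turn 30-minute successes into primary failures

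*SAP*

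**What the plan says.** SAP 4.1, under post-dose assessments, states: "Plasma glucose levels and assessments of neuroglycopenic symptoms will be censored after the time of drug administration". The next sentence limits this: "This censoring is applicable only if the insulin is" "restarted prior to the 180 minutes timepoint as per the following language in the protocol".

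The protocol text reproduced there comes from Protocol 10.2.1.2 (Preparation and Administration of Study Drug, item 8). It lets the investigator start insulin or another medical intervention before 180 minutes if glucose is rising, and advises against doing so before 90 minutes. It gives insulin, carbohydrates and a meal as examples. Its censoring rule is: "Plasma glucose data and assessments of neuroglycopenic symptoms will be censored after the time of intervention, per the statistical analysis plan".

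SAP 5.3.6.2.1, among the rules for incomplete pharmacodynamic data, says: "If insulin starts after receiving glucagon, the glucose values post insulin start will be censored out and considered as missing". It adds: "This is also considered a major protocol deviation". SAP 5.1.3 keeps subjects with major deviations out of the per-protocol population.

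The primary endpoint (SAP 5.3.6.1) is read within 30 minutes of injection. SAP 6.5 says: "Subjects who are missing the primary endpoint for a study treatment will be considered as having a failure in the primary analysis". This applies to ITT and mITT, and a sensitivity analysis counts missing data as success. Non-inferiority requires an upper 95% limit for the difference in failure rates of at most 5%, with a G-Pen failure rate of at most 5%.

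**The concern.** The SAP gives two incompatible starting points for the same censoring. Its period definitions in 5.2 use drug administration to mean the study drug, so on its ordinary meaning the 4.1 sentence discards every post-dose glucose and neuroglycopenic value once insulin is restarted early. That includes the 30 minutes on which the primary endpoint is judged. Early intervention is allowed because glucose is rising, so the subjects affected would tend to be those in whom glucagon worked.

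The rule also covers only part of the questionnaire. Secondary endpoints 8 and 9 use autonomic symptoms and the overall feeling of hypoglycemia, and the SAP also analyses a total score built from all eight items. No text says what happens to these after an intervention.

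**Working it through.** **1. The start points side by side**

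| Place | Censoring starts at | Trigger | Variables named |
|---|---|---|---|
| SAP 4.1, own sentence | study drug administration | insulin restarted before 180 min | glucose, neuroglycopenic |
| Protocol 10.2.1.2, quoted in SAP 4.1 | intervention | insulin or other medical intervention (examples include carbohydrates, a meal) | glucose, neuroglycopenic |
| SAP 5.3.6.2.1 | insulin start | insulin after glucagon | glucose |

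The start points disagree, and so do the triggers. No row covers the autonomic score (AAS), the total score (ATS) or the overall-feeling question.

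**2. One subject.** Suppose glucose rises by 20 mg/dL or more within 30 minutes and insulin is started at 120 minutes. Under the second and third rows, all values up to 120 minutes stay and the subject is a success. Under the first row, every value after injection is removed, the primary endpoint is missing, and SAP 6.5 scores a failure in ITT and mITT. The missing-as-success analysis scores a success. In the per-protocol set the subject is absent, because SAP 5.3.6.2.1 makes the insulin a major deviation.

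**3. How many such subjects would matter.** The documents state no figure that depends on this rule, so there is nothing to reproduce. They also give no rate of early insulin, so the counts below are assumptions.

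Inputs: n = 122 per treatment (SAP 4.2); no true failures (assumed); *a* erased results on G-Pen and *b* on GlucaGen. The interval is the unpaired Wald interval, the default of the riskdiff code in SAP Appendix 2:

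U = (p₁ − p₂) + 1.96 × √[p₁(1 − p₁)/n + p₂(1 − p₂)/n], with p₁ = a/n and p₂ = b/n.

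- a = 3, b = 0: p₁ = 3/122 = 0.0246; SE = √(0.0246 × 0.9754/122) = 0.0140; U = 0.0246 + 0.0275 = 0.052.
- a = b = 6: p₁ = p₂ = 6/122 = 0.0492; SE = √(2 × 0.0492 × 0.9508/122) = 0.0277; U = 0 + 0.0543 = 0.054.

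| Erased on G-Pen | Erased on GlucaGen | G-Pen failure rate | Upper limit | Both criteria met? |
|---|---|---|---|---|
| 2 | 0 | 1.6% | 3.9% | yes |
| 3 | 0 | 2.5% | 5.2% | no |
| 5 | 5 | 4.1% | 5.0% (just inside) | yes |
| 6 | 6 | 4.9% | 5.4% | no |
| 12 | 12 | 9.8% | 7.5% | no |

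The 5% limit on the G-Pen rate alone allows at most 6 failures (6/122 = 4.9%; 7/122 = 5.7%).

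If censoring starts at the intervention, insulin at 90 to 180 minutes erases 0 primary results.

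**4. The uncovered symptom data.** The total score averages all eight items (SAP 5.3.6.2.2). After an intervention, its four neuroglycopenic items are censored and its four autonomic items are not, and the SAP does not say how the score is then formed. Symptom relief, complete resolution and the first answer of No on the overall question are mostly times to a first event (SAP 5.3.6.2.3). Protocol 6.4 reports peak symptom relief at about 30 minutes in XSGP-301. With intervention not recommended before 90 minutes, few first events should come after it.

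**The case against.** The strongest defence is that the 4.1 sentence announces itself as carrying out the protocol rule printed beneath it, and that rule says intervention. SAP 5.3.6.2.1 agrees on the start point for insulin. Section 4.1 describes the design, while the sections that define and analyse the primary endpoint (5.3.6.1 and 6.5) contain no such censoring. SAP 2 promises to identify substantial differences from the protocol, and SAP 10 lists only the move to time-to-event methods. Discarding a whole profile because of an event 90 or more minutes after dosing would also be an odd choice. All this stands, and it makes a drafting slip the likely explanation.

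It does not remove the problem. The protocol rule refers back to the SAP, and the SAP says it supersedes the protocol's statistical considerations. The rule with the consistent start point sits among pharmacodynamic conventions. The only general post-dose censoring statement in the SAP's own words is the faulty one.

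Two further points against the concern also stand. The neuroglycopenic-only wording comes from the protocol and was carried into the SAP. And insulin given for rising glucose would not be expected to relieve hypoglycemia symptoms, so a reader should not infer that it credits study drug with false relief. The more plausible route is glucose or food, including the oral or IV glucose that Protocol 7.3 provides for when glucose has risen by less than 20 mg/dL at 30 minutes. SAP 4.1's insulin-only trigger does not reach that case.

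**Conclusion.** The inconsistency is real and should be corrected before database lock, because one of the two start points can reach the primary endpoint. A reader might infer that the plan does erase the 30-minute result of anyone given later insulin, or that non-inferiority is therefore likely to fail. The documents do not support that. The adjacent protocol quotation and SAP 5.3.6.2.1 both point the other way, and no rate of early insulin is given.

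The risk is one of literal programming. If it happened, three erased results on G-Pen alone, or six on each treatment, would be enough to miss the margin with no true failures. That rests on 122 subjects per treatment, the unpaired Wald interval and missing counted as failure. It is confined to ITT and mITT and would be reversed in the missing-as-success analysis.

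The gap for autonomic, total and overall-feeling data is a separate, smaller point, probably with little effect on endpoints 8 and 9.

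A further contradiction needs resolving: the protocol permits post-glucagon insulin, while SAP 5.3.6.2.1 calls it a major deviation, which under SAP 5.1.3 removes the subject from the per-protocol set.

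**What to change.** In SAP 4.1, change the censoring start from drug administration to intervention and set out one rule, for example: *If a listed intervention is given before 180 minutes after study drug, all plasma glucose values and all hypoglycemia questionnaire results (ANS, AAS, ATS and overall feeling) recorded after the time of that intervention are censored. Values recorded before it, including those in the 0-30 minute window, are retained.*

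With it:

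- List the triggering interventions once, and make SAP 4.1 (insulin only) agree with the protocol text it quotes (also other medical intervention, carbohydrates or a meal).
- Say how the rule works if glucose or dextrose under Protocol 7.3 is given within the primary window, so that values affected by rescue are not kept by accident.
- Refer SAP 5.3.6.2.1 and 5.3.6.2.3 to this rule instead of restating it.
- Reconcile Protocol 10.2.1.2 with SAP 5.3.6.2.1 on whether post-glucagon insulin is a major protocol deviation, and state the consequence for the per-protocol population.

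The start-point correction is a wording change in the SAP. Extending the rule to all questionnaire items goes beyond the protocol's wording, so the SAP should identify it as a difference. The price is slightly more censoring in the autonomic, total and overall-feeling analyses.
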